11.2 Sample Size and Accrual

This is a pilot trial to gather the data necessary to plan a randomized phase II study with a control group receiving standard therapy. The planned accrual is 80 evaluable patients over two years. An evaluable patient is a patient that has received their complete prescribed treatment (including those whose ICG measurements or ALBI precluded the second phase of treatment and those for whom other toxicity prevented them from receiving a full course of treatment). The high level goal of this trial is to define an individualized and adaptive approach to use of RT in this patient population. Key components of individualizing and adapting treatment are models that relate expected toxicity and tumor control outcomes to RT dose and other patient level characteristics. Part of the reason for the sample size of 80 is to refine these models prior to initiating a randomized trial. For toxicity, our preliminary data suggests that mean liver dose (or some other measure of dose to normal liver), baseline liver function (e.g. CP score) and mid-treatment change in ICGR15 are the most important factors. If our overall event rate for toxicity is about 20%, we expect to have approximately 16 toxicity events which, in combination with some data from similarly treated previous patients, should be sufficient to estimate parameters in a toxicity model with 3 predictors. For tumor control, tumor dose is expected to be the most significant predictor. There will likely be a lower rate of local progression events so that this model may need to have fewer predictors. In addition to further defining statistical models this trial will permit us to estimate rates of toxicity and tumor control that will be key when designing a randomized trial with power to reject a specific null hypothesis.

This treatment will be considered sufficiently promising to initiate a phase II trial if it causes toxicity (increase in CP score of 2 points or more within 6 months of treatment) in no more

than 25% of patients and results in a local control rate (at 1 year) of at least 80%.

We expect to be able to accrue 20 patients per year and thus to complete accrual in approximately 4 years.

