11.0 STATISTICAL CONSIDERATIONS

11.1 Study Design

This is a pilot study of individualized adaptive RT, which consists of 3/5 of a planned total course of treatment, a one month break, assessment of global and spatial liver function change using IC-Green or ALBI, and perfusion MRI, and the remainder of treatment adjusted for global and spatial changes in liver function. The primary endpoints are to establish the feasibility of this approach and to obtain preliminary estimates of safety and efficacy both overall and as they relate to treatment and patient characteristics. At the completion of this trial we will have the necessary data to define a SBRT treatment approach that is individualized and adaptive and ready to be compared to standard SBRT in a randomized trial.

Patients will have an initial plan with total dose chosen such that the estimated probability of toxicity (increase in CP of 2 points or more within 6 months of RT) from the first three of five planned treatments is at most 10%. In order to protect the safety of individual patients, after delivering 60% of the planned total treatment, there will be a 1 month break at the end of which, ALBI or ICG will be measured again and a new treatment plan will be developed.

This last course of treatment may be adapted (relative to the first course) globally in one of 2 ways. First, if there is no remaining enhancement on the MRI scan, no further radiation will be given because the tumor is likely to be cured. The second possible adaptation is intended

to prevent clinically significant decline in liver function in patients whose livers appear to be sensitive to RT. Child-Pugh (CP) score is a standard measure of liver function, and an increase of 2 points or more on this scale is considered clinically significant. Early changes in ICG retention and ALBI reveal subclinical changes in liver function that predict later liver toxicity, assessed by a change of 2 in CP score 6 months after treatment.

Maximizing tumor control and minimizing liver toxicity are competing objectives when selecting RT dose for these patients. To make this tradeoff explicit and quantitative, the dose during the second course of treatment will be selected as the minimum of

- 1) The dose that maximizes $\text{Prob}(\text{Local Control at 1 year}) - 4 * \text{P}(\text{Toxicity})$
- 2) The dose associated with a 25% estimated risk of toxicity.

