That is, additional dose is deemed to be beneficial if the increase in local control is at least 4 times greater than the increase in toxicity. The key advantage of this approach over an isotoxic approach is that patients are exposed to risk of toxicity in direct proportion to their benefit in terms of increased local control. Thus patients are not unnecessarily exposed to higher rates of toxicity (e.g. 20%) unless the improvement in expected local control is large enough. Similarly, patients are not constrained to an arbitrary rate of toxicity (e.g. 15 or 20%) if allowing the rate of toxicity to exceed this threshold results in a large enough increase in local control. At the same time we still place a hard upper limit of 25% on the risk of toxicity to any patient. The overall rate of toxicity in this population of patients is expected to be lower than 25%.

In the above, toxicity is defined as increase in CP of 2 points or more within 6 months of RT and local control is defined as absence of tumor progression within 1 year of treatment. For purposes of this dose selection, local control will be estimated from a simple Cox model as a function of tumor dose while the toxicity model will include the change in ICGR15 at the mid-treatment timepoint.

The decision to continue treating patients with further radiation is based on analysis of the information from the ICG results or ALBI, and not RECIST measurements. These measurements are recommended and are not required to determine patients' coming off-study treatment or study protocol. In addition, baseline measurements are not needed at the time of enrollment.

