11.3 Data Analysis Plans

Primary Aims: The first primary aim is feasibility which is defined as the ability to successfully deliver the full treatment including all adaptations and in particular the perfusion based planning and replanning. In the simplest analyses, feasibility will simply be summarized as the proportion of patients for whom the intended treatment was feasible. The reasons for lack of feasibility for any patients will be investigated individually.

The primary efficacy endpoint is local control, measured as the time to progression of the treated lesion. Patients with no evidence of local progression at the time of data analysis will be censored at the last date on which they were evaluated for local progression. Local progression will be summarized with Kaplan-Meier curves. The estimated rate of local control at 6, 12, 18 and 24 months will be estimated and reported with 95% confidence intervals. Cox regression models will be used to assess the relation between the hazard of local progression and tumor dose and other covariates.

The primary toxicity endpoint is defined as a change in Child Pugh score of greater than or equal to 2 within 6 months of SBRT. Secondary toxicity endpoints include changes in ALBI scores and grade 3 toxicities described in section 8. RILD is a rare but serious side effect that will also be summarized if it occurs. Logistic regression models will be used to estimate the association between baseline (primarily baseline liver function such as CP score and mean liver dose and other dose metrics such as D700) and mid-treatment variables (e.g. change in ICGR15) and the probability of toxicity. We will include interactions between dose and baseline liver function as there is some evidence that patients with worse liver function are more sensitive to radiation than patients with better baseline liver function.

Secondary Aims: The relation between various biomarkers and treatment efficacy will be assessed by including the biomarkers as covariates in Cox regression models for local progression. The relation between biomarkers and toxicity will be assessed in logistic regression models for the binary or ordinal toxicity outcomes and linear regression models for continuous measures of toxicity or liver function such as ICGR15 or ALBI.

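### The sample size is argued for a 3-predictor toxicity model, but the analysis plan commits to a larger one, by logistic regression with no shrinkage or validation stated and earlier data of unstated size

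*Combined protocol and SAP*

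**What the plan says.** Section 11.2 (Sample Size and Accrual) sets the size: "The planned accrual is 80 evaluable patients over two years". It continues: "If our overall event rate for toxicity is about 20%, we expect to have approximately 16 toxicity events". These events, "in combination with some data from similarly treated previous patients", "should be sufficient to estimate parameters in a toxicity model with 3 predictors". The three predictors it has in mind are a measure of dose to normal liver, baseline liver function, and the mid-treatment change in ICGR15. The same section gives refinement of the toxicity and control models before a randomized trial as part of the reason for 80 patients.

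Section 11.3 (Data Analysis Plans) fits toxicity by logistic regression on baseline and mid-treatment variables. The dose terms are left open: "mean liver dose and other dose metrics such as D700". It then adds: "We will include interactions between dose and baseline liver function". It states no cap on the number of terms, no penalty or prior, and no internal validation.

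Section 5.1.4 says that data accumulating in the trial will update the individualization model, without giving a method. Section 1.1.4 allows ALBI in place of ICG.

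**The concern.** The sufficiency argument covers one model and the analysis plan commits to another. Each interaction costs a slope, as does each extra dose metric, and neither is counted in 11.2. The argument also rests on earlier data whose size, event count and method of combination are not stated, so a reader cannot check it.

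With few events per slope, an ordinary logistic fit gives predicted risks that are too spread out: low risks too low and high risks too high. That matters here because the fitted model is one of the trial's products. It is meant to refine individualized dosing and to be carried into the next trial.

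**Working it through.** **1. The plan's own figure.** Inputs from 11.2: 80 evaluable patients, 20% toxicity. Expected events = 80 × 0.20 = 16. This reproduces the stated figure.

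**2. Events per slope, trial data only.** Three main effects (11.2) plus at least one interaction (11.3) make at least 4 slopes.

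| Toxicity rate | Events (80 × rate) | 3 slopes | 4 slopes | 6 slopes |
|---|---|---|---|---|
| 10% | 8 | 2.7 | 2.0 | 1.3 |
| 15% | 12 | 4.0 | 3.0 | 2.0 |
| 20% | 16 | 5.3 | 4.0 | 2.7 |
| 25% | 20 | 6.7 | 5.0 | 3.3 |

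The 6-slope column allows for two additional terms, such as another dose metric or a second interaction.

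**3. Variation in the event count.** For a binomial with n = 80 and a true rate of 20%, the 95% range is 9 to 23 events and P(at least 16) = 0.55. At 15% that probability is 0.14.

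**4. Expected-shrinkage formula.** n = p / [(S − 1) ln(1 − R²/S)], where p is the number of slopes, S the expected shrinkage and R² the Cox-Snell value. At 20% toxicity the maximum R² is 1 − exp{2(0.2 ln 0.2 + 0.8 ln 0.8)} = 0.632. I assume that the model reaches 15% to 35% of this, so R² runs from 0.095 to 0.221.
- At n = 80, S is 0.73 to 0.87 with 3 slopes, 0.67 to 0.84 with 4, and 0.58 to 0.78 with 6.
- For S = 0.9, n is 107 to 270 with 3 slopes and 142 to 360 with 4.

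**5. Simulation, maximum likelihood against ridge.** Assumptions: four standardized terms with log-odds 0.6, 0.5, 0.6 and 0.2 (the last being the interaction), 20% toxicity, and a ridge penalty of 2. Each fit is evaluated on a large independent population. The pooled sizes are assumptions: 156 = 80 + the 76 patients that 1.1.4 mentions from the preceding trial, and 180 = 80 + 100.

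| Patients | Median slope, maximum likelihood | Median slope, ridge |
|---|---|---|
| 80 | about 0.67 | about 0.89 |
| 156 to 180 | about 0.82 to 0.86 | about 0.93 to 0.97 |

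Across these settings ridge lowers the root-mean-square error of predicted risk by about 0.4 to 1.6 percentage points. The gain is largest at 80 patients.

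**6. Sensitivity to predictor strength.** A second design uses three true predictors, with a c-statistic of about 0.66 to 0.80, fitted by maximum likelihood at 80 patients and 16 events. The median slope is 0.58 to 0.77 with 3 slopes, 0.51 to 0.73 with 4, and 0.39 to 0.61 with 6. With 4 slopes at 180 patients and 36 events it is 0.74 to 0.87.

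**The case against.** The strongest reply is that 11.2 does not rest on 16 events alone. A reader might infer that it does, but the sentence makes sufficiency depend on pooling with earlier patients, and pooling helps: under the assumed sizes the slope rises from about 0.67 to 0.82–0.86. This stands as a limit on the claim. Overfitting is likely, not certain, and its degree depends on data that the plan does not describe. The absence of a penalty is likewise inferred from silence.

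Three stronger readings are tempting, and the documents do not support them.

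- *The trial's dose limits rule out 16 events.* Section 11.1 limits the estimated risk "from the first three of five planned treatments is at most 10" percent, and adds that "additional dose is deemed to be beneficial if the increase in local control is at least 4 times greater than the increase in toxicity". If so, mean toxicity is at most 10% plus a quarter of the control gain, and 20% would need a gain of (20 − 10) × 4 = 40 points. But that bound needs calibrated models and the current 10% rule for all 80 patients. Section 1.1.4 indicates that up-front individualization followed an analysis of the first 20 evaluable patients. The endpoint also counts any Child-Pugh rise of 2 or more, with no attribution to radiation, and 11.2 states 20% conditionally. Fewer than 16 events is possible, but no contradiction is shown.
- *The 11.3 fit itself is what is held against the 10% and 25% limits in this trial.* No section says so. Section 5.1.4 bases the first part on the existing NTCP model. The links are its model-update sentence and the aim in 11.2 of refining the models.
- *Overfitting is what puts patients predicted just under 25% above that limit.* In the simulation at 20% toxicity the share whose true risk exceeds 25% is about the same with ridge as with maximum likelihood, so it is not evidence for this point. Section 11.1 already words the dose rule in terms of estimated risk; only its later summary sentence is loose.

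It is also fair to say that a pilot with no hypothesis test has latitude in modelling, and that the coefficients and penalty used above are choices. The mismatch between 11.2 and 11.3 does not depend on them.

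**Conclusion.** The point holds in this form: 11.2 does not justify the model that 11.3 commits to, and the earlier data on which it relies cannot be assessed. The mismatch follows from the text alone: 3 predictors against at least 4 slopes, so 4.0 or fewer trial events per slope at the assumed 20% rate.

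The size of the overfitting rests on assumed coefficients, an assumed penalty and assumed pooled sizes. Within those, unpenalized predictions are too extreme, markedly so on the trial data alone and moderately so after pooling; pooling reduces the problem without removing it. Ridge was better calibrated and more accurate in each setting in the comparison. A further unquantified loss is that ICGR15 change will be missing for patients assessed by ALBI, so a model using it may have fewer than 80 patients and 16 events.

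This should be corrected in the plan. It does not undermine the trial's descriptive estimates of toxicity and local control.

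**What to change.** In 11.2:
- Count the interaction terms, and any extra dose metrics, as parameters.
- State how many earlier patients and toxicity events will be pooled, and how.
- Say that events could fall below 16 if toxicity is under 20%, or if ICGR15 is missing because ALBI was used.

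In 11.3:
- Fit the toxicity model by penalized logistic regression: either ridge, or a Bayesian model with a prior from the earlier patients and a study intercept. Shrink the interaction.
- Report an optimism-corrected calibration slope.

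The cost is wording, standard software and a little more analysis work, with no extra patients. The downside is slightly shrunken coefficients.

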11.3 Data Analysis Plans

Primary Aims: The first primary aim is feasibility which is defined as the ability to successfully deliver the full treatment including all adaptations and in particular the perfusion based planning and replanning. In the simplest analyses, feasibility will simply be summarized as the proportion of patients for whom the intended treatment was feasible. The reasons for lack of feasibility for any patients will be investigated individually.

The primary efficacy endpoint is local control, measured as the time to progression of the treated lesion. Patients with no evidence of local progression at the time of data analysis will be censored at the last date on which they were evaluated for local progression. Local progression will be summarized with Kaplan-Meier curves. The estimated rate of local control at 6, 12, 18 and 24 months will be estimated and reported with 95% confidence intervals. Cox regression models will be used to assess the relation between the hazard of local progression and tumor dose and other covariates.

The primary toxicity endpoint is defined as a change in Child Pugh score of greater than or equal to 2 within 6 months of SBRT. Secondary toxicity endpoints include changes in ALBI scores and grade 3 toxicities described in section 8. RILD is a rare but serious side effect that will also be summarized if it occurs. Logistic regression models will be used to estimate the association between baseline (primarily baseline liver function such as CP score and mean liver dose and other dose metrics such as D700) and mid-treatment variables (e.g. change in ICGR15) and the probability of toxicity. We will include interactions between dose and baseline liver function as there is some evidence that patients with worse liver function are more sensitive to radiation than patients with better baseline liver function.

Secondary Aims: The relation between various biomarkers and treatment efficacy will be assessed by including the biomarkers as covariates in Cox regression models for local progression. The relation between biomarkers and toxicity will be assessed in logistic regression models for the binary or ordinal toxicity outcomes and linear regression models for continuous measures of toxicity or liver function such as ICGR15 or ALBI.

Quality of life will be summarized descriptively at baseline (pre-RT) and at each post RT timepoint. Change from baseline will be calculated for each patient and summarized descriptively as well as tested for statistical significance using a paired t-test.

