2.2 Secondary Objectives

- 1) To collect data on biomarkers of treatment efficacy, toxicity, and liver function to plan further enhancements to individualized RT.
- 2) To determine the change in quality of life during and after RT.

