5.1.1.2 Baseline bloodwork and physical exam to obtain ALBI and Child Pugh score

5.1.1.3 Regional functional assessment with perfusion MRI

MRIs will be obtained by trained personnel in the Department of Radiation Oncology at the University of Michigan.

5.1.1.3.1 Evaluations will occur within 4 weeks prior to the start of RT, at approximately 4-6 weeks after the completion of the first 3/5 of planned treatments, and approximately 1-3 months after RT is completed.

5.1.1.3.2 For patients scheduled to have perfusion MRI for other reasons (including prior or subsequent enrollment in this or other protocols), every effort will be made to use results for both purposes, to avoid duplication, including extending windows by an extra 4 weeks in each direction.

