6.0 STUDY PROCEDURES

6.1 Screening/Baseline Procedures

Assessments performed exclusively to determine eligibility for this study will be done only after obtaining informed consent. Assessments performed for clinical indications (not exclusively to determine study eligibility) may be used for baseline values even if the studies were done before informed consent was obtained.

All screening procedures must be performed within 30 days prior to registration unless otherwise stated. Baseline procedures to be completed prior to radiotherapy. The screening procedures include:

- 6.1.1 Informed Consent
- 6.1.2 Medical history
- 6.1.3 Review subject eligibility criteria
- 6.1.4 Physical exam: To include ascites and encephalopathy
- 6.1.5 Performance status
- 6.1.6 Baseline adverse event assessment
- 6.1.7 Hematology: CBC
- 6.1.8 Serum chemistries: Comprehensive metabolic panel (CMP) to include: albumin, alkaline phosphatase, ALT, AST, BUN, creatinine, electrolytes (sodium, potassium), glucose, and total bilirubin.
- 6.1.9 Coagulation assessment: PT/INR
- 6.1.10 Tumor assessment: The longest dimension of each tumor to be treated will be measured and recorded either on the most recent diagnostic scan or simulation scan.
- 6.1.11 Indocyanine green or ALBI baseline testing: ICG retention or ALBI will be measured by blood test after study enrollment and prior to radiotherapy.
- 6.1.12 Blood draw for correlative studies after study enrollment and prior to radiotherapy. See Section 10.0 for details.
- 6.1.13 For patients who consent to this portion of the study, tumor biopsy will also be performed (see section 10.1.2) after study enrollment and prior to radiotherapy.

Generally, this would be performed at the time of clinically necessary fiducial placement for radiation targeting.

6.1.14 Quality of life assessment after study enrollment and prior to radiotherapy: FACT-HEP (Version 4).

6.2 Procedures During Treatment: See section 5

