6.3 Follow-Up Procedures

Patients will be evaluated approximately 1 month after completion of therapy and then at approximately 3-6 month intervals until 2 years. Evaluation will include H&P, laboratories (CBC, comprehensive metabolic panel, INR, AFP if elevated at diagnosis), and liver imaging (beginning 3 months after treatment). QOL assessments will be obtained at the same intervals for 1 year. ICG or ALBI will be assessed approximately 1 and 3 months after completion of therapy. Blood and urine (when patient is able to provide) will be collected at approximately 1 and 3 months after completion of therapy. MRI will be assessed approximately 1 month after completion of therapy. This follow up schedule will adhere to standard of care clinical follow up. Therefore, missed visits and visits that diverge from this regimen will not be considered protocol deviations. MRI and ICG must be performed at the University of Michigan. However, if patients are not able to travel for all other follow up evaluations and procedures, they may have these performed by a local physician and records obtained by the study team. If patients are concurrently or previously enrolled in another research study which requires similar testing, all efforts will be made to avoid unnecessary repeat testing.

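### The linear biomarker models for ICGR15 and ALBI leave timepoint, outcome form and baseline adjustment unstated, so a marker of existing cirrhosis could pass for a marker of radiation injury

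*Combined protocol and SAP*

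**What the plan says.** The Secondary Aims paragraph of section 11.3 describes the biomarker analyses briefly. For categorical outcomes: "The relation between biomarkers and toxicity will be assessed in logistic regression models for the binary or ordinal toxicity outcomes". For continuous outcomes: "linear regression models for continuous measures of toxicity or liver function such as ICGR15 or ALBI". Neither statement gives a timepoint or an adjustment covariate, and the second does not say whether the outcome is a level or a change.

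Other parts of the plan bear on this:

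- **Primary toxicity model (11.3).** Among its predictors are baseline variables, described as "primarily baseline liver function such as CP score and mean liver dose and other dose metrics such as D700", with dose-by-baseline interactions.
- **ALBI as an endpoint (11.3).** "Secondary toxicity endpoints include changes in ALBI scores and grade 3 toxicities described in section 8". No similar wording makes change in ICGR15 an outcome; it appears as a predictor.
- **Baseline data.** Section 6.1.11: "ICG retention or ALBI will be measured by blood test after study enrollment and prior to radiotherapy". Section 5.1.1.2: "Baseline bloodwork and physical exam to obtain ALBI and Child Pugh score".
- **Follow-up data (6.3).** "ICG or ALBI will be assessed approximately 1 and 3 months after completion of therapy".
- **Purpose (2.2).** "To collect data on biomarkers of treatment efficacy, toxicity, and liver function to plan further enhancements to individualized RT". Section 1.5.1 adds that circulating markers are to be examined for what they contribute to judging liver injury, with a view to adjusting liver dose.

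**The concern.** Baseline liver function varies widely by design. Section 3.1.8 admits Child-Pugh A to B7 with tumors over 3.5 cm, and B8 and above with any tumor size. Section 1.1.3 notes that most patients with HCC also have cirrhosis. A post-treatment ICGR15 or ALBI therefore carries much of what was already there before radiation. Circulating cytokines may vary with existing liver disease too. A regression of the later value on the biomarker then mixes two things: an association with pre-existing function, and the response to radiation that the toxicity question is about.

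At stake is which markers go forward to individualize dose in later work. A marker that only restates baseline ALBI would add nothing to a value already in the chart, yet it could be selected.

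**Working it through.** The plan gives no power, effect size, standard deviation or correlation for these models, so there is no figure of its own to reproduce.

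**Inputs.** n = 80 evaluable patients (11.2). Assumed: two-sided test at 0.05; r = correlation of biomarker with baseline value, 0 to 0.5; rho = correlation of baseline with follow-up value, 0.5 to 0.9; equal variances at both times. The biomarker is given no effect on the follow-up value once baseline is known, so every significant result is false.

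**Spurious correlation created by each outcome**

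- Level: r × rho.
- Change: (r × rho − r) / √(2(1 − rho)) = −r × √((1 − rho)/2).
- Level with baseline as covariate: 0.

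The change score gives the opposite sign. Patients who start worse tend to regress toward the mean, so a marker of poor baseline function appears to go with less decline. That is equally misleading.

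**False-positive rates at n = 80** (10,000 simulated trials per row)

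| r | rho | Level | Change | Level + baseline |
|---|---|---|---|---|
| 0.2 | 0.5 | 14.3% | 14.4% | 5.1% |
| 0.2 | 0.7 | 23.3% | 10.5% | 5.3% |
| 0.2 | 0.9 | 36.0% | 6.8% | 5.1% |
| 0.3 | 0.5 | 26.7% | 27.2% | 4.8% |
| 0.3 | 0.7 | 46.6% | 17.8% | 4.6% |
| 0.3 | 0.9 | 68.7% | 9.1% | 4.7% |
| 0.5 | 0.5 | 62.4% | 61.3% | 4.9% |
| 0.5 | 0.7 | 90.0% | 41.1% | 4.7% |
| 0.5 | 0.9 | 98.9% | 16.8% | 4.8% |

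At r = 0 all three analyses stay between 4.6% and 5.3%.

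**Check by formula.** With d = atanh(|correlation|) × √(n − 3), the rate is 1 − Φ(1.96 − d) + Φ(−1.96 − d). For the level at r = 0.2, rho = 0.5, the correlation is 0.10 and d = 0.1003 × √77 = 0.88, which gives 14.2%. For change at r = 0.2, rho = 0.9, the correlation is −0.2 × √0.05 = −0.045 and d = 0.39, which gives 6.8%. Both agree with the simulation.

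**Smaller sample.** ICG is used only in some patients. If 40 had it (an assumption), the rates for r of 0.2 to 0.5 are 8.7% to 84.8% for the level, 6.1% to 34.5% for change, and about 5% with baseline as a covariate.

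**Precision when r = 0.** Adjustment multiplies residual variance by 1 − rho². Power becomes Φ((z + 1.96)/√(1 − rho²) − 1.96), where z is the normal quantile of the unadjusted power. From 80%, this gives 83.6%, 89.9% and 97.5% at rho = 0.3, 0.5 and 0.7. From 50%, it gives 53.8%, 61.9% and 78.4%.

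**The case against.** A reader might infer that the plan regresses the post-treatment level and leaves baseline out. The documents do not say that; they are silent. Where ALBI is a toxicity endpoint, 11.3 speaks of changes, section 2.3.1.2 sets its ALBI threshold alongside a change in Child-Pugh score, and section 5.2 also uses a change. A change outcome is therefore a fair reading for ALBI. The Secondary Aims paragraph is also shorthand. Its Cox sentence adds biomarkers to a model type already described, and the toxicity models could be meant the same way, with baseline function already in them. That is plausible but not written.

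A second tempting inference is that such a marker will look like a marker of injury. That holds only if it correlates with baseline function, and the documents give no figure for that. At r = 0 the problem disappears.

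Third, the stated aim covers liver function as well as toxicity. For association with liver function itself, a level outcome is no error.

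All three points stand and limit the claim, but they do not remove it. Nothing in the documents supplies baseline adjustment for these models. Nothing makes change in ICGR15 an outcome. And the change reading still leaves false-positive rates of 6.8% to 61.3% over the assumed range.

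**Conclusion.** The point holds as a gap in specification with a conditional consequence. The linear ICGR15 and ALBI models lack a timepoint, an outcome form and a baseline covariate. If either unadjusted form is used for the toxicity question, false-positive rates could be well above 5%: about 14% to 99% for the level and 7% to 61% for change at n = 80. These ranges rest entirely on the assumed r and rho. They also treat the measured baseline as carrying all pre-existing function; if it is measured with error, adjustment would reduce the inflation but not remove it all.

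The consequence is small in scope. This is a secondary biomarker aim of a pilot, and the criteria in 11.2 for going on to phase II (Child-Pugh change and one-year local control) are untouched. It is worth changing because the better model needs nothing the trial does not already collect.

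**What to change.** In the Secondary Aims paragraph of 11.3, for the toxicity question, write:

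> Linear regression of ICGR15 or ALBI at each stated post-baseline time, with the patient's pre-RT value of the same measure as a covariate and the biomarker as the term of interest.

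Name the times. Fit ALBI in every patient with the needed laboratory values; albumin and bilirubin are in the baseline chemistry panel (6.1.8), and a metabolic panel is drawn at follow-up (6.3). Fit ICGR15 only in patients who had both tests.

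Do not add delivered mean liver dose as a routine covariate. Sections 5.1.2.3 and 11.1 adapt the second part of treatment to mid-treatment liver function, so delivered dose partly reflects the response under study, and conditioning on it can bias the biomarker coefficient.

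Unadjusted association with the level of liver function may still be reported, separately and labeled as descriptive.

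The cost is one clause and one degree of freedom in a model with up to 80 patients. No new data are needed.
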